2.3 Patient disposition, demographics and other baseline characteristics

Demographic and other baseline data including baseline disease characteristics will be summarized descriptively by treatment group and preceding study for all subjects in the ENR set and the subjects included in the FAS set. Categorical data will be presented as frequencies and percentages. For continuous data, mean, standard deviation, median, minimum, and maximum will be presented. For selected parameters, 25th and 75th percentiles will also be presented.

Information from all enrolled subjects, including subjects who complete only first observation period and do not transition into the first half of the treatment period, will be provided in a listing. Information on screen-failed subjects will not be included in the summaries of demographics, disease characteristics at baseline, and medical history.

2.3.1 Demographics (collected at Screening Visit 1)

- Age
- Age group (adolescents (12-17 years), adults (18 - 65 years, ≥ 65 years))
- Sex
- Race
- Ethnicity
- Weight
- Height

- Body Mass Index (BMI) – calculated as weight (kg) / (height (m))²
- BMI group (< 25, 25 - < 30, >= 30 kg/m²)

2.3.2 Disease characteristics at baseline (baseline is defined in Section 2.1.1.4)

- CU Index category
- [REDACTED]
- Baseline UAS7 score
- Duration of CSU – collected at Visit 201
- Baseline AAS7 score
- Baseline proportion of AAS7 = 0
- Type of prior urticaria medication – collected at Visit 201

2.3.3 Medical History

Relevant medical histories and current medical conditions collected from preceding study baseline before patients received any study drug will be reported. Urticaria related medical history will be summarized by system organ class and preferred term, by treatment group and preceding study in the FAS set. Summaries for urticaria-specific medical history will be provided in a descriptive manner as well. Other medical history will be listed.

2.3.4 Patient disposition

The following will be presented based on the ENR set by overall and preceding study and preceding study treatment group:

- The number and percentage of subjects who complete the screening period will be presented. In addition, the reasons for screen failures will be provided.
- The number and percentage of subjects who enter and completed the first observation period (OBS1) will be presented. In addition, the reasons for discontinuation in OBS1 will be provided.

Patient disposition during treatment, observation, and follow-up periods will be listed. The following will be presented based on the FAS set by overall and treatment group defined in section 2.1.1.1:

- The number and percentage of subjects who entered, completed, and discontinued TRT1A (including the reason for discontinuation)
- The number and percentage of subjects who entered, completed, and discontinued TRT1B (including the reason for discontinuation)
- The number and percentage of subjects who entered, completed, and discontinued TRT2 (including the reason for discontinuation)

- The number and percentage of subjects who entered, completed, and discontinued OBS2 (including the reason for discontinuation)
- The number and percentage of subjects who entered, completed, and discontinued 52-week FU (including the reason for discontinuation)
- The number and percentage of subjects who entered, completed, and discontinued 12-week FU (including the reason for discontinuation)

In addition, duration of study periods TRT1, OBS2, TRT2, FU12 and FU52 will be summarized by treatment group for FAS; duration of study period OBS1 will be summarized for ENR. *Duration in weeks* will be calculated as (the date of the study period end date - the date of the study period start date + 1) / 7.

Note that the end date of each study period is defined as below:

- OBS1 (only applicable for subjects who enter OBS1): max (OBS1 disposition date, last visit end date) and (101<=last visit number <199)
- TRT1 (only applicable for subjects who enter TRT1): max (TRT1 disposition date, last visit end date) and (201<=last visit number <214)
- OBS2 (only applicable for subjects who enter OBS2): max (OBS2 disposition date, last visit end date) and (301<=last visit number <319)
- TRT2 (only applicable for subjects who enter TRT2): max (TRT2 disposition date, last visit end date) and (last visit number in (214, 401-412))
- FU12 (only applicable for subjects who enter FU12): study disposition date
- FU52 (only applicable for subjects who enter FU52): max (study disposition date, last visit end date) and (501<=last visit number <9999)

2.4 Treatments (study treatment, rescue medication, concomitant therapies, compliance)

2.4.1 Study treatment / compliance

The analysis of treatment will be performed based on the SAF for relevant study periods and by treatment groups. Categorical data will be summarized as frequencies and percentages. For continuous data, mean, standard deviation, median, 25th and 75th percentiles, minimum, and maximum will be presented.

The number of patients and the duration of exposure to each treatment will be as indicated in Table 2-7. Duration of exposure is defined as the date of the last treatment minus the date of first treatment in the extension study plus 4 weeks (28 days). For example, duration of exposure of ligelizumab 120 mg q4w liquid in vial is defined as: the date of last injection of ligelizumab 120 mg q4w liquid in vial – the date of the first injection of ligelizumab 120 mg q4w liquid in vial +28 days. Likewise, duration of exposure of ligelizumab 120 mg q4w PFS is defined as:

the date of last injection of ligelizumab 120 mg q4w PFS – the date of the first injection of ligelizumab 120 mg q4w PFS +28 days.

In addition, the number of doses per patient that are correctly administered per protocol, and number of missed doses will be presented. A partial dose will be considered as if 100% of the dose of the assigned treatment has been administered.

At interim and final analyses, treatment exposures will be summarized as needed.

Table 2-7 Treatment exposures evaluated in relevant study periods

Treatment	Study period
ligelizumab 120 mg q4w (liquid in vial)	TRT1A
ligelizumab 72 mg q4w (liquid in vial)	TRT1A
ligelizumab 120 mg q4w (PFS)	TRT1B, TRT1B+TRT2
ligelizumab 120 mg q4w (PFS+ outside-of-clinic self-administration)	TRT1B, TRT2
ligelizumab 120 mg q4w (PFS+monotherapy)	TRT2
ligelizumab, SAF	TRT1A+ TRT1B+TRT2

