3.4 Second observation period

- Visit 301 (Week 0) to 399 (Week 52 also referred to as End of Observation Period 2, EOBS2).
- If the subject's UAS7 is ≤ 6 at Week 52, the subject will enter the second (investigational treatment-free) observation period Visit 301 (Week 0) and will be assessed remotely (i.e. outside the clinic) by a safety phone call from the site every 4 weeks, unless there is an in-clinic visit scheduled.
- Subjects will have in-clinic safety and efficacy assessments done at 12 or 16 week intervals.
- Subjects must remain on the same H1-AH background medication they were taking in the preceding studies.
- Subjects should use the same H1-AH rescue medication that was agreed with the investigator at Visit 1 of this study.
- Use of oral corticosteroid rescue medication is **not permitted** during this second observation period.

- Subjects will continue to complete the eDiary twice daily as per protocol, in order to monitor the activity of their disease. All subjects should complete their eDiary for the 7 days prior to Visit 214 (i.e. one assessment-week) to ensure the UAS7 thresholds are available.
- Subjects who present with moderate to severe active disease ($UAS7 \geq 16$) will be brought back to clinic to be treated as soon as possible to perform Visit 214 (Week 52) in the second half of the treatment period) and restart treatment with ligelizumab 120 mg PFS q4w.
- Subjects with a $UAS7 < 16$ by the end of this second observation period will perform Visit 399 (EOOBS2) of this extension study to exit the study.
- Subjects who wish to discontinue from this observation period will be expected to complete at least Visits 301, 302 and 303 (Week 0, 4 and 8), and perform Visit 399 (Week 52/EOOBS2) and exit the study.

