6.1.4 Treatment duration

As described above in [Section 3](#) and [Section 4.2](#), the longest possible treatment is 104 weeks however this treatment might not be continuous and might span over a period of 156 weeks due to possibly entering the observation period.

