12.3 Treatments

The Safety set will be used for the analyses below. Categorical data will be summarized as frequencies and percentages. For continuous data, mean, standard deviation, median, 25th and 75th percentiles, minimum, and maximum will be presented.

The number of subjects and the duration of exposure to investigational drug and dose will be summarized by treatment. Duration of exposure is defined as the date of the last treatment minus the date of first investigational drug administration plus 4 weeks (28 days).

In addition, the number of doses, total cumulative dose, and number of missed doses will be presented. A partial dose will be considered as if 100% of the dose of the assigned treatment has been administered.

Concomitant medications and significant non-drug therapies prior to and after the start of the study treatment will be listed and summarized according to the Anatomical Therapeutic Chemical (ATC) classification system. Concomitant medications will be summarized for the safety set separated for urticaria related background medications and non-urticaria related medications. Similarly, use of rescue medication will also be summarized.

[figure not shown]

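### In the two pooled rows of SAP Table 2-7, the first-to-last-dose formula counts the treatment-free second observation period as exposure for every subject who restarts

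*SAP*

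**What the plan says.** **The rule.** SAP 2.4.1 defines duration of exposure as "the date of the last treatment minus the date of first treatment in the extension study plus 4 weeks" (28 days). Its worked example for the pre-filled syringe takes the last PFS injection date and subtracts "the date of the first injection of ligelizumab 120 mg q4w PFS +28 days". Protocol 12.3 agrees: "Duration of exposure is defined as the date of the last treatment minus the date of first investigational drug administration plus 4 weeks".

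**Where it is applied.** SAP Table 2-7 lists the periods for which exposure is summarised. PFS exposure is shown for "TRT1B, TRT1B+TRT2", and ligelizumab in the safety set for "TRT1A+ TRT1B+TRT2". The second PFS entry and the safety-set row each join the two treatment halves.

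**What lies between the halves.** Under Protocol 3.4, with UAS7 of 6 or less at Week 52, "the subject will enter the second (investigational treatment-free) observation period Visit 301 (Week 0"). Protocol 3.3 also lets subjects with UAS7 above 6 and below 16 move there after a risk-benefit discussion. Subjects who relapse to UAS7 of 16 or more restart at Visit 214. SAP 2.1.1.2 caps OBS2 at 52 weeks and defines TRT2 so that Visits 301 to 399 are left out.

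**What the protocol says about length.** Protocol 6.1.4 puts the longest treatment at 104 weeks and adds that "this treatment might not be continuous and might span over a period of 156 weeks".

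**The concern.** Last dose minus first dose plus 28 days measures treated time only if dosing runs without a break. This design builds in a break for some subjects and then lets them restart. For them, a subtraction across both halves returns the calendar span and labels it exposure.

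The error runs one way: it can only lengthen reported exposure. What is at stake is the descriptive statement of how much ligelizumab and PFS treatment time the study accumulated. A reader would take that figure as treated time.

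**Working it through.** **Inputs**
- Dosing every 4 weeks, 13 doses per half (Protocol 6.6.1).
- First-half doses at Weeks 0 to 48, the last at Visit 213, Week 48 (Protocol 3.3).
- PFS from Week 12 (Protocol 3.3), so 10 of the first 13 doses are PFS.
- Second-half doses nominally at Weeks 52 to 100 (Protocol Table 8-1), moved later by the OBS2 length *g* weeks for a restarter.
- *g* at most 52 (SAP 2.1.1.2).

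The 28-day credit after the Week 48 dose ends at Week 52, where OBS2 begins. On this schedule none of OBS2 is covered by the credit.

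**Reproducing the protocol's own figures**
- No gap: 100 − 0 + 4 = 104 weeks, the longest treatment in Protocol 6.1.4.
- Gap of 52 weeks: (100 + 52) − 0 + 4 = 156 weeks, the calendar span in Protocol 6.1.4.

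For a full-length restarter, the exposure formula therefore returns what the protocol calls the span.

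**Formula as written, both halves completed**
- All ligelizumab: (100 + *g*) − 0 + 4 = 104 + *g*.
- PFS: (100 + *g*) − 12 + 4 = 92 + *g*.

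**Formula applied within each half, then added**
- All ligelizumab: (48 − 0 + 4) + (100 − 52 + 4) = 52 + 52 = 104 weeks, whatever *g* is. Check: 26 doses × 4 = 104.
- PFS: (48 − 12 + 4) + (100 − 52 + 4) = 40 + 52 = 92 weeks. Check: 23 doses × 4 = 92.

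The excess is *g* in both rows.

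| OBS2 length *g* (weeks) | All ligelizumab, as written vs 104 | PFS, as written vs 92 |
|---|---|---|
| 0 | 104 (0%) | 92 (0%) |
| 12 | 116 (+11.5%) | 104 (+13.0%) |
| 26 | 130 (+25.0%) | 118 (+28.3%) |
| 36 | 140 (+34.6%) | 128 (+39.1%) |
| 52 (maximum) | 156 (+50.0%) | 144 (+56.5%) |

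**Restarters cut short.** Fewer second-half doses leave the excess in weeks unchanged but raise it in relative terms. With one restart dose:
- After a 12-week gap, the dose falls at Week 64: 64 + 4 = 68 weeks as written, against 52 + 4 = 56 (+21%).
- After a 52-week gap, it falls at Week 104: 104 + 4 = 108, against 56 (+93%).

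**Average error.** Across the safety set, the mean excess is the share of subjects who restart times their mean OBS2 length. The documents give neither, so no average can be stated.

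**The case against.** **The plan evidently means to leave OBS2 out.** The Table 2-7 labels omit it, SAP 2.1.1.2 removes Visits 301 to 399 from TRT2, and where the SAP wants the rest period counted it names OBS2 in the label, as in Table 2-16. This stands as evidence of intent. It does not change the arithmetic, because a first-to-last subtraction covers everything between the two dates and no instruction says to add within periods. A programmer must depart from the formula or from the label.

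**Other outputs show the gap.** The number of doses (SAP 2.4.1), the separate durations of TRT1, OBS2 and TRT2 (SAP 2.3.4) and the cumulative dose (Protocol 12.3) are all planned. True, so the gap is not hidden, but the duration would then disagree with those summaries without explanation.

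**The study stopped early.** The 52-week gap followed by a full second half is a design limit. SAP 2.14.1 drops even the uninterrupted 104-week population because of termination. This stands against presenting +50% or +57% as expected results. It does not remove the point: SAP 2.14.3 applies Section 2.4 to the final analysis, and SAP 2.14.1 keeps the subpopulation treated with a rest. SAP 2.4.1 does say exposure is summarised as needed at that stage, so the pooled rows may not all be produced.

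**A stronger reading.** A reader might infer that the long-term adverse event rates are diluted too. The documents do not support that. SAP 2.8.1.2 gives the exposure-adjusted rate its own time (to first event, or to last follow-up), does not refer to 2.4.1, and deliberately uses the whole period after first treatment for cardio-cerebrovascular and malignancy events. The long term treatment subpopulation excludes anyone who entered OBS2. For restarters, Table 2-16 reports adverse events, serious events and events leading to discontinuation by single period.

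**Conclusion.** The point holds, within limits. The formula gives the wrong quantity in two rows of SAP Table 2-7 for subjects who restart after OBS2. Rows confined to TRT1A, TRT1B or TRT2 are unaffected, as are subjects who never restart.

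The overstatement per restarter equals the OBS2 length, at most 52 weeks. This assumes nominal 4-weekly dosing with the last first-half dose at Week 48; if that dose is missed, the untreated gap is longer than OBS2. The full-length maxima, 156 against 104 and 144 against 92 weeks, are theoretical after early termination, and the average effect cannot be determined from the documents.

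The consequence is a mislabelled descriptive exposure summary. The primary endpoint is untouched, and no effect on the exposure-adjusted incidence rates should be assumed. It merits correction because the error is definite, one-directional and cheap to remove.

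**What to change.** Add to SAP 2.4.1: for any subject with a Visit 301, exposure in a row of Table 2-7 that joins TRT1 (or TRT1B) and TRT2 is the sum of last dose minus first dose plus 28 days, computed separately within each treatment half, with OBS2 excluded. Apply this to the PFS TRT1B+TRT2 entry and to the ligelizumab safety-set row.

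Protocol 12.3 carries the same formula, so record the change in SAP Section 4, which is now marked as not applicable.

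The cost is one sentence in 2.4.1, an entry in Section 4 and a small programming change. It uses dose dates that the present formula already needs; no new data are required.

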2.4.2 Prior and concomitant therapies

2.4.2.1 Prior medications

Prior medications which were taken and stopped prior to first dose of study treatment in preceding studies will not be re-summarized for extension study, as they have been summarized in the preceding studies.

Prior medications for CSU which were taken after V1999 of preceding studies and stopped prior to first dose of study treatment in the extension study will be summarized based on SAF by treatment group. Prior medications for CSU will be summarized by type of therapy, preferred term, and treatment group.

2.4.2.2 Concomitant medications and non-drug therapies

Concomitant medications are defined as any medication given at least once between the first dose of the study treatment and the date of the last study visit in the extension study.

Concomitant medications will be listed and summarized based on SAF by treatment group, separately for urticaria related background medications and non-urticaria related medications, by the Anatomical Therapeutic Chemical (ATC) code and preferred term (PT).

The concomitant medication tables will be provided for the treatment periods, observation periods, and the entire study period separately, by treatment group defined in section 2.1.1.

The summary tables will be provided for the following:

- TRT1A: the first 12 weeks of the first half of the treatment period (up to Visit 204)

- TRT1B: week 13 to week 52 in the first half of the treatment period (up to Visit 214 or 301, whichever comes first)
- OBS2: the second observation period
- TRT2: the second treatment period
- FU: the follow-up period

Similarly, significant non-drug therapies will be listed.

2.4.2.3 Concomitant use of rescue medication

If unbearable symptoms occur during the study, subjects will be instructed by investigators on the acceptable treatment (H1-AH and oral corticosteroid) for managing their disease with the use of rescue medication.

Fexofenadine, loratadine, desloratadine, cetirizine, levocetirizine and rupatadine H1-AHs, in addition to being allowed as background medication, will be allowed as rescue medication and used on an as-needed basis during all study periods (i.e. screening, observation, treatment and follow-up).

In addition, after the Week 12 (Visit 204) primary endpoint, subjects will be permitted to use oral corticosteroids such as prednisone and its equivalents as rescue medication if needed.

2.4.2.3.1 Concomitant use of rescue medication based on eCRF

Concomitant use of rescue medication (using eCRF information) will be summarized and listed by study period based on the starting date, by ATC code and preferred term as indicated in **Table 2-8** below.

Table 2-8 Study periods for rescue medications

	H1-AH	Oral Corticosteroid
SCR	×	
OBS1	×	
TRT1A	×	
TRT1B	×	×
OBS2	×	
TRT2	×	×
12-week FU	×	×
52-week FU	×	×

2.4.2.3.2 Concomitant use of rescue medication in eDiary

The number of tablets taken, and name of rescue medication (H1-AH and oral corticosteroids) used over the past 24 hours for controlling CSU conditions (such as itch or hives) is recorded once daily in the eDiary by the patient.

The total weekly number of tablets of rescue medication from the eDiary data will be summarized by study week. Median with quartiles will be displayed graphically over time to describe the score change during the study periods. The total weekly number of tablets of rescue medication will be calculated as the sum of the number of tablets per day, over 7 days.

If rescue medication use was not recorded (due to not completing the eDiary entry) on one or more days over the week, then the total weekly number of tablets will be missing.

2.4.2.4 Prohibited medication

The use of prohibited medication in study will be captured by PDs.

2.5 Analysis of the primary objective

This section will detail the statistical analysis of the primary endpoint. Details of the hypothesis testing strategy, including primary and secondary endpoints to handle multiplicity, are provided in Section 2.6.

2.5.1 Primary endpoint

The primary endpoint is the proportion of subjects with well-controlled urticaria, defined as Weekly Urticaria Activity Score (UAS7) ≤ 6 , at Week 12 (Visit 204) in the first half of the treatment period.

The analysis of primary endpoint will be performed on the subjects whose preceding study is CQGE031C2302 or CQGE031C2303 (i.e. the two core studies) and received ligelizumab treatment with same dose regimen.

2.5.1.1 Primary estimand

Subjects who discontinue from study treatment early will be encouraged to stay in the study following the procedures described in the protocol Section 9.1.1. These are considered as retrieved drop-out (RDO) subjects. To be noted, if the patients take unplanned study treatment (e.g., Omalizumab) in the follow-up period after study treatment discontinuation, the efficacy data collected after that will not be considered as RDO data and will be excluded from analysis.

The definition of primary estimand is described by the following attributes.

- **Population:** Adult and adolescent participants receiving H1-antihistamines therapy at local-approved dose level as background medication suffering from chronic spontaneous urticaria and meeting study inclusion/exclusion criteria, who were rolled over from the previous pivotal studies (CQGE031C2302 and CQGE031C2303).
- **Variable:** the proportion of subjects with well-controlled urticaria (UAS7 ≤ 6) at Week 12

- **Treatment of interest:** ligelizumab retreatment after rolling over from the pivotal studies (CQGE031C2302 and CQGE031C2303) with stable H1-antihistamines (H1-AH) at local-approved doses as background medication + allowed rescue medication, if needed.
- **Handling of intercurrent events:**
 1. Discontinuation of initially assigned study treatment prior to Week 12 due to adverse events (AE) or lack of efficacy (LoE) or any other reasons except for the reason of study early termination: Participants who discontinue from study treatment early will be encouraged to stay in the study. RDO data collected after study treatment discontinuation will be used for analysis. (*treatment policy strategy*).
 2. Discontinuation of initially assigned study treatment prior to Week 12 due to study early termination: had participants not discontinued treatment prior to Week 12 study termination (*hypothetical strategy*)
 3. Use of rescue medication prior to Week 12: ignore (*treatment policy strategy*).
- **The summary measure:** the proportion of subjects with well-controlled urticaria ($UAS7 \leq 6$) at Week 12 for each treatment arm.

